3.6. Variables

a) Demographic variables

- **Age** expressed in years (y)
- **Sex** Male (M)/ Female (F)
- **Weight** expressed in IMC
- **Ethnic**: Caucasian/ African/ Asiatic/ American
- **Tobacco**: YES / NO / EX-Smoker
- **Age of UC diagnosis** expressed in years (y)
- **Familiar Antecedents** (YES/NO) which kind of disease?

b) Clinical variables:

- **Mayo Clinical Score** (*Clinical colitis activity index*) (Schroeder KW *et al.*

NEngl J Med 1987; 317: 1625-9). Punctuation range: 0-9 punts.

- **Rome IV Criteria** (Lacy BE, Mearin F, Chang L, *et al.* Bowel disorders. *Gastroenterology* 2016;150:1393-407).

- **IBS- SSS** (*Irritable Bowel Syndrome – Symptom Severity Score*) (Almansa C *et al.* *Rev Esp Enferm Dig* 2011 Dec;103 (12):612-8.

- **HADS** (*Hospital Anxiety and Depression Scale*) (Johnston M, *et al.* *J Psychosom Res* 2000;48:579-84.9)

- **Escala de Likert**: Subjective valuation of improvement of symptoms after the intervention

- **Adherence to Mediterranean Diet Questionnaire** (Estruch R *et al* *NEJM* 2013).

c) Analytical parameters:

Haemoglobin: blood haemoglobin concentration (g/dl).

Albumin: blood albumin concentration (g/dl).

Triglycerides: blood triglycerides concentration (mg/dl).

Cholesterol: blood cholesterol concentration (mg/dl).

C-reactive protein: blood C-reactive protein concentration (mg/dl).

Faecal calprotectin: faecal calprotectin concentration (µg/g).

d) Variables Microbiològiques

The microbiological profile of the microbiota of these patients will be analysed through high-throughput sequencing before and after the intervention.

3.7. Methods

The proposed study will include 96 patients with UC in remission (Mayo Index ≤ 2 and Calprotectin ≤ 250 µg/gr), over 18 years of age, who have signed informed consent, who meet Rome IV criteria and present a moderate-severe severity index will be included (IBS-SSS >175). These patients will be randomized to one of the two intervention arms (N=48 per group):

- Treatment group: traditional bread (200g daily).
- Control group: modern bread (200g daily).

For both intervention groups stool and blood samples will be collected before starting the intervention (Visit 0 - Basal), and then after 8 weeks (Final Visit). The monitoring period will be 8 weeks. In addition, we will collect demographic data (age, sex, smoking habit, etc.), clinical data (Mayo index, Rome IV, IBS-SSS, CVE 20, HADS, PCR Likert scale, VSG, albumin, hemoglobin, faecal calprotectin, etc.), and microbiological variables.

The intervention will last 8 weeks and the following visits will be made during the study:

1. Consent- Pre-Randomization Visit

The patient will be evaluated by a doctor from the Gastroenterology service at the University Hospital [name] who will explain the study and evaluate the inclusion and exclusion criteria. Participants will be able to ask all the questions they have about it before signing the written consent. If the potential volunteer wishes to participate, after reading the informative documentation and receiving the relevant explanations, he must carefully read the informed consent and if he agrees with it he must sign it.

The patient will be provided with the 2 containers necessary to collect the stool sample at home for the following visits

2. Baseline Visit (V₀)

The patient will come to the visit with the stool sample corresponding to the basal Visit (V₀) before the intervention.

The demographic variables (age, sex, weight, ethnicity, smoking habit, family history, etc.) will be collected, the different established questionnaires and indexes will be completed (Rome IV, Mayo, IBS-SSS, CVE-20, HADS), and a blood test will be performed (PCR, Calprotectin, blood count, etc.).

The patient will be randomized and the bread will be provided according to the randomization result to intervention A or B. The patient will be told that he can collect the following portions of bread at the centre 1 or 2 times a week, for the next 8 weeks of intervention.

3. End of study Visit (EOS; W8)

The patient will come to the visit, 8 weeks later, with the stool sample corresponding to the final visit (VF) of the study.

The various established questionnaires and indexes will be performed (Rome IV, Mayo, IBS-SSS, CVE-20, HADS, Likert scale), and a blood test will be performed (PCR, Calprotectin, blood count, etc.).

The evolution of the patient's symptoms will be assessed after 8 weeks of the intervention, and a new medical assessment will be carried out.

3.8. Microbiological analysis

The stool samples collected at V₀ and VF will be stored at -80°C at the Biomedical Research Institute of Girona (IdIBGi). Before the microbiological analyses, the genomic DNA of the 16S RNA gene will be extracted using the commercial NucleoSpin® Soil Kit (Machery-Nagel GmbH & Co., Germany). The DNA concentration will be determined with the Qubit® BR kit (Invitrogen). The microbiological profile of the microbiota of these patients will be analyzed through mass sequencing by the subcontracted company StarSEQ. The region corresponding to the V3-V4 variable region of the 16S rRNA gene will be sequenced using specific primers (e.g., 515F/806R, [Caporaso et al Nat Method 2010]) and Illumina HiSeq200 technology through paired-end reads (generating 300bp sequences).

3.9. Statistical analysis

All statistical analyses will be performed using R software (2.14.0, <http://www.r-project.org/>). Pearson's chi-squared test will be used to determine whether there is a statistically significant difference between demographics and questionnaire data with more than one category. Normality for numerical data will be assessed through the Shapiro-Wilk test. For data with normal distribution, a paired t-test will be used to determine whether there is a statistically significant difference, whereas, for data with non-normal distribution, the Wilcoxon signed-rank exact test will be used. Significance levels will be established for $p \leq 0.05$.

Alpha diversity indices together with beta-diversity matrices will be computed by groups of intervention. Normality will be assessed through the Shapiro-Wilk test, and statistical differences in each treatment group will be analysed using Welch two sample t-test or paired t-test for data with normal distribution and Wilcoxon rank sum exact test or Exact Wilcoxon Signed-Rank test for data with non-normal distribution. For beta diversity matrices, unweighted Unifrac, weighted Unifrac and Bray-Curtis distances will be computed and plotted through principal coordinate analyses (PCoA).

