2.2 Objectius

To compare in vivo the influence of 2 types of bread, one long-fermented and one short-fermented, on the clinic and intestinal microbiota of patients with quiescent Ulcerative Colitis (UC), with symptoms compatible with IBS (Rome IV Criteria).

Specific objectives:

- To determine changes in the overall gut microbiota composition in patients with quiescent UC, before (V0) and after 8 weeks (VF) of the intake of traditional bread.
- To determine the correlation between the changes observed in the composition of the intestinal microbiota in V0 and VF and the clinical condition of the patient with quiescent UC.
- Assess the impact of traditional bread versus modern bread on improving the clinical response of patients with quiescent UC.

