3.5. Randomization

Participants will be assigned to one of the two interventions using a random sequence separated by sex. It will remain double-blind throughout the study. In the case of withdrawal or abandonment of a participant, the new subject will be assigned a consecutive number and the intervention he will receive will be assigned using the same random sequence separated by sex as the rest of the participants.

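### The only test the clinical analysis paragraph leaves for the final-visit Likert improvement scale is Pearson's chi-squared, which ignores the order of the categories

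*Combined protocol and SAP*

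**What the plan says.** Section 3.6 lists the Likert scale among the clinical variables and describes it as "Subjective valuation of improvement of symptoms after the intervention". It does not give the number of response levels.

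Section 3.7 sets the schedule. At the baseline visit the instruments are "Rome IV, Mayo, IBS-SSS, CVE-20, HADS". At the final visit they are "Rome IV, Mayo, IBS-SSS, CVE-20, HADS, Likert scale". The Likert scale is in the second list only.

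The first paragraph of section 3.9 covers the clinical data. It applies Pearson's chi-squared to test for a "difference between demographics and questionnaire data with more than one category". For numerical data it says: "For data with normal distribution, a paired t-test will be used to determine whether there is a statistically significant difference"; non-normal numerical data get the Wilcoxon signed-rank test. The second paragraph covers microbiota diversity, and the two-sample tests (Welch's t and Wilcoxon rank-sum) are named only there.

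One specific objective in section 2.2 is a comparison between arms: "Assess the impact of traditional bread versus modern bread on improving the clinical response". Under section 3.5, patients are "assigned to one of the two interventions using a random sequence separated by sex".

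**The concern.** A rating of improvement has ordered categories, and the question put to it is directional: do patients given traditional bread report more improvement than those given modern bread? Pearson's chi-squared returns the same value however the categories are arranged. It therefore tests for any difference in distribution, and its sensitivity to a consistent shift is diluted over k-1 degrees of freedom.

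Two things are at stake. A real shift toward improvement is more likely to be missed. And a significant chi-squared does not by itself show that one bread did better, because a difference in spread alone can produce it. The Likert item is the patient's own rating of improvement, so it bears directly on the clinical-response objective.

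**Working it through.** **Which test applies.** The scale is recorded once per patient, so neither the paired t-test nor the signed-rank test can compare V0 with the final visit, and neither compares two independent arms. The rank-sum test is assigned to diversity indices. Of the tests in the clinical paragraph, only chi-squared remains.

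**Inputs.** From the protocol: 48 per arm (section 3.7) and significance level 0.05 (section 3.9). Assumed: a two-sided test, since sidedness is not stated; 3, 4, 5 or 7 levels, since the number is not stated; a rating from every patient; and a proportional-odds shift in the simulations. The plan gives no figure for this comparison, so there is none to reproduce.

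**Order is ignored.** Take an illustrative table with 48 per arm and five levels from worst to best: 4, 8, 16, 12, 8 against 10, 14, 14, 7, 3. Chi-squared is 7.93 on 4 df, p = 0.094, and is identical after the columns are shuffled. The rank-sum test on the same table gives p = 0.005.

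**Analytic power.** An ordinal test spends 1 df, and 80% power at two-sided 0.05 needs noncentrality (1.960 + 0.842)² ≈ 7.85. If the same shift is tested by chi-squared on k-1 df, power is the probability that a noncentral chi-squared variable with k-1 df and noncentrality 7.85 exceeds the 5% critical value. The sample size that restores 80% is 48 × (noncentrality needed on k-1 df) / 7.85, calculated unrounded and then rounded up.

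| Levels | df | Chi-squared power | Loss relative to 80% | Noncentrality for 80% | n per arm for 80% |
|---|---|---|---|---|---|
| 3 | 2 | 70.9% | 11% | 9.63 | 59 |
| 4 | 3 | 64.5% | 19% | 10.90 | 67 |
| 5 | 4 | 59.5% | 26% | 11.94 | 73 |
| 7 | 6 | 52.1% | 35% | 13.62 | 84 |

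For example, with 3 levels: (0.800 - 0.709) / 0.800 = 11%, and 48 × 9.63 / 7.85 = 58.9, so 59.

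**Simulation at 48 per arm.** 200,000 replicates, with the odds ratio set so that the rank test has 80% power.

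| Levels | Base distribution (%) | OR | Chi-squared power | n per arm for 80% |
|---|---|---|---|---|
| 3 | 25/50/25 | 2.99 | 70.8% | 59 |
| 4 | 15/35/35/15 | 2.88 | 63.7% | 67 |
| 5 | 10/20/40/20/10 | 2.85 | 57.4% | 74 |
| 7 | 5/10/15/40/15/10/5 | 2.83 | 47.7% | 86 |

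Skewed base distributions give 71.4%, 63.3%, 57.5% and 48.3%. With no difference between arms, rejection is 4.2-5.3% for chi-squared and 4.9-5.1% for the rank test, so both hold their level.

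**Smaller effect.** A separate simulation (10,000 replicates, other base distributions) at OR 2 gives chi-squared against rank-sum power of 36% against 45% with 3 levels, 26-29% against 46-47% with 5, and 22-24% against 47-49% with 7.

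**Difference without direction.** Five levels, 10/20/40/20/10% in one arm and 20% in each level in the other, so both have the same centre: chi-squared is significant in 50% of trials and the rank test in 5%.

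**The case against.** The strongest objection is that the plan never assigns chi-squared to this item. Section 3.9 does not name the Likert scale, its phrase about questionnaire data is tied to no instrument, and it does not say whether the scale is categorical or numerical. Scored as a number, the scale would have no usable between-arm test in the clinical paragraph. On this view the analysis is unspecified rather than wrong. It stands that the assignment is an inference. But either reading needs the same sentence in 3.9, and following the text as written leads to chi-squared.

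A second objection is that the gap is wider: with paired tests only, IBS-SSS and HADS also have no between-arm test. That is fair, but a general repair for numerical outcomes would not settle how an ordered rating is handled.

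Third, clinical response is not defined, and the Likert item is not ranked as an endpoint. This limits the weight of the point.

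Fourth, the power figures rest on assumed levels and on odds ratios near 3, for which the documents give no support; at OR 2 the rank test itself has less than 50% power. This changes the size of the loss but not its existence.

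Finally, chi-squared is a valid test, and the example without direction is not a false positive, because the two distributions do differ. Direction can be read from the table afterwards. The example shows only that significance alone does not establish benefit.

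**Conclusion.** The concern holds. Where an ordinal test would have 80% power, using chi-squared costs about 9 percentage points with 3 levels, 16 with 4, 20 with 5 and 28 with 7 by the analytic calculation. Simulation gives slightly larger losses with 5 and 7 levels. The loss appears at every number of levels tried and at the smaller odds ratio. The type I error is not affected.

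This rests on reading the Likert item as categorical questionnaire data, on the assumed numbers of levels, on a two-sided test with 48 ratings per arm, and on a difference that is a shift along the scale. Confidence is medium because the assignment of the test is inferred. The plan should be changed, but the point does not threaten the trial's validity.

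**What to change.** In section 3.9, before unblinding:

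- State the number of Likert levels.
- Compare the final-visit rating between arms with a Wilcoxon rank-sum test stratified by sex, or with a proportional-odds model containing arm and sex. Sex is included because randomisation is separated by sex; the power figures above are for unstratified tests.
- Report the common odds ratio with its 95% CI, so that direction and size are both visible.
- Keep Pearson's chi-squared, or Fisher's exact test, for nominal items.

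The cost is a sentence or two and no extra data; the rank-sum test is already named in 3.9 for alpha diversity. There are two small downsides. An ordinal test is less sensitive to differences that are not a shift (5% against 50% in the example above), and the model assumes proportional odds.

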3.2. Inclusion criteria

- > 18 years of age
- Patients diagnosed with ulcerative colitis according to established clinical and histological criteria as common clinical practice
- Remission of ulcerative colitis defined as a total Mayo score ≤ 2 and faecal calprotectin values under 250 ng/g
- Moderate-to-severe IBS-like symptomatology defined by Rome IV criteria and IBS Symptom Severity Score (IBS-SSS) > 175

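### Section 3.9 lets a Shapiro-Wilk result choose between t-tests and rank tests without fixing what is checked or what is estimated, so the test and its target can differ between outcomes and possibly between arms

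*Combined protocol and SAP*

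**What the plan says.** Section 3.9 of the combined protocol and SAP sets a two-step rule for numerical outcomes. First, "Normality for numerical data will be assessed through the Shapiro-Wilk test". Outcomes that pass this check go to a paired t-test. The plan's wording for those that fail it is: "for data with non-normal distribution, the Wilcoxon signed-rank exact test will be used". The significance threshold is p ≤ 0.05.

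The next paragraph of 3.9 repeats the normality check for the alpha diversity indices, where "statistical differences in each treatment group will be analysed using Welch two sample t-test or paired t-test", with the rank-sum and signed-rank tests as the non-normal alternatives.

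Four things are not stated:

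- whether the check is applied to raw visit values or to the within-patient change;
- whether it is applied per arm or pooled (3.9 refers to each treatment group only for the diversity indices);
- what threshold the check uses;
- whether the target is a mean change or another measure of location.

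Nothing requires both arms to be analysed with the same test.

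**The concern.** A paired t-test addresses the mean change. A signed-rank test addresses the pseudo-median of the changes, which equals the mean only when the changes are symmetric. A rule that moves between them on the trial's own data therefore moves between questions, and nobody can say before the data are seen which question a given outcome will answer. If the check is run per arm, one arm's result may concern a mean and the other's a pseudo-median, although section 2.2 sets out to compare traditional with modern bread.

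What is checked also matters. The entry criteria restrict baseline values ("IBS Symptom Severity Score (IBS-SSS) > 175" in section 3.2, and upper limits on Mayo score and calprotectin). A truncated baseline can fail a normality check even when the change, which is what the paired t-test uses, is close to normal.

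**Working it through.** **Inputs from the documents.** 48 patients per arm and measurements at V0 and week 8 (section 3.7); threshold 0.05 and the two-step rule (section 3.9).

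**Assumptions.** Two-sided tests; Shapiro-Wilk threshold 0.05; the check applied to changes, separately in each arm; skewed changes drawn from a gamma distribution shifted to true mean zero. The documents give no distributional data, so the skewness values show a range and are not estimates.

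**Stated level.** The only error rate in 3.9 is the nominal 5%. With normal changes the two-step rule returns 5.0%, so the nominal level is reproduced in that case.

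**Step 1: do the arms get the same test?** Let q be the probability that Shapiro-Wilk rejects in one arm. With the same distribution in both arms, P(different tests) = 2q(1 − q).

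- Normal: q = 0.052, so 2 × 0.052 × 0.948 = 0.099.
- Skewness 0.5: q = 0.214, so 2 × 0.214 × 0.786 = 0.336.
- Skewness 1.0: q = 0.670, so 2 × 0.670 × 0.330 = 0.442.
- Skewness 2: q = 0.999, so 2 × 0.999 × 0.001 = 0.002.

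Mismatch is greatest at moderate skewness and disappears when skewness is strong, because both arms then go to the signed-rank test.

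**Step 2: false-positive rate for a mean change of zero, within one arm of 48** (20,000 simulated arms per row; the 1.4 row shows the range over separate runs)

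| Changes | Two-step rule | Signed-rank always | t-test always |
|---|---|---|---|
| Normal | 5.0% | 4.9% | 4.8% |
| Laplace (symmetric) | 5.1% | 5.0% | 4.9% |
| t, 3 df (symmetric) | 5.2% | 5.1% | 4.7% |
| Skewness 0.5 | 5.8% | 6.0% | 5.0% |
| Skewness 1.0 | 8.7% | 8.7% | 5.2% |
| Skewness 1.4 | 12.0-14.0% | 13.4-13.9% | about 5.5-6.3% |

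For the skewed rows the first two columns nearly coincide, so the excess belongs to the signed-rank test, not to the act of pre-testing. With 40 per arm, skewness 0.5 and 1.0 give 5.9% and 8.7% for the two-step rule.

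**Step 3: the two-sample version (Welch or rank-sum).** Equal means, skewness 1.0-1.4. If the arm SDs are 1 and 1.5, the rule rejects in 8-12% of trials, against about 5% for Welch throughout. If the SDs are equal, it rejects in 4.8-4.9%.

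**Step 4: raw values or changes.** Baseline IBS-SSS was drawn from a normal parent (assumed mean 250-300, SD 60-80) and kept only above 175. In arms of 48, Shapiro-Wilk then fails in about 5% (mean 300, SD 60) to 50% (mean 250, SD 80). With an assumed visit correlation of 0.5-0.7 and no bread effect, the change has skewness between −0.01 and −0.04 and fails in only about 5% of arms. For the same data, the unstated choice of what to check can therefore decide the test.

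**Step 5: the proposed kind of analysis.** A between-arm Welch test of change held 4.8-5.4% across normal, gamma (skewness 1 and 2) and lognormal changes. A linear model with covariate adjustment held 4.6-5.4% under the skewness values examined.

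**The case against.** The strongest reply is that a reader might infer more than 3.9 supports, in four ways.

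- *That the error rate exceeds 5% as a matter of course.* It does not. The excess needs skewed changes together with a true mean change of exactly zero, and the plan never names the mean as its target. If bread changes nothing and the two visits are exchangeable, changes are symmetric and the signed-rank test is valid even for skewed raw data (4.8% for lognormal visits).
- *That the normality check causes the inflation.* Step 2 shows that using the signed-rank test throughout gives almost the same rates.
- *That the rank test is used precisely when symmetry fails.* Shapiro-Wilk also rejects symmetric heavy-tailed changes (62% of arms for t with 3 df, 51% for Laplace), where the signed-rank test is sound.
- *That the baseline cut at 175 feeds the inflation for IBS-SSS.* It does not, because the change is close to normal. In one truncated example with no bread effect, the rule rejected in 14.2% and the plain t-test in 14.0%. That excess is regression to the mean within an arm, which removing the check alone would not cure.

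All four limits stand. The exchangeability argument, however, does not cover every outcome, because entry restricts V0 and not week 8. With lognormal calprotectin (assumed parent median 50-100, log-SD 0.8-1.0, visit correlation 0.5-0.7), a baseline cut at 250 and no bread effect, changes have skewness 1.6 to 4.6. Mean and median change then differ (21.6 against 6.7 in one case), so the two tests answer different questions.

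It is also fair to say that the level of the check and the data checked are ambiguities, not demonstrated errors. That within-arm tests cannot answer a between-arm objective is a separate matter and adds no weight here.

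**Conclusion.** The point holds as a specification gap with a conditional effect on error rates. Section 3.9 leaves the test, the data checked and the quantity tested to be settled by the trial's own data.

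Mismatched tests between arms (about 10% of trials with normal changes, 34-44% at skewness 0.5-1.0) require that the check is made per arm, which 3.9 indicates only for the diversity indices. False-positive rates of about 6%, 9% and 12-14% require skewed changes (0.5, 1.0 and 1.4, all assumed) and a mean target. The 8-12% for the two-sample version requires the arms to differ in spread as well. The documents do not support a claim that the rule inflates error in general, or that inflation and mismatch peak together. The change is still worth making, since it removes the ambiguity at no cost in data.

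**What to change.** In section 3.9:

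1. Delete the normality check as a means of choosing the test.
2. For each numerical outcome, prespecify one between-arm analysis: a linear model of the week-8 value on arm, baseline value and sex (the randomisation stratum in section 3.5).
3. State the target quantity, for example the adjusted difference in means at week 8.
4. Fix any transformation of skewed laboratory values, such as calprotectin and C-reactive protein, before unblinding.
5. Report a rank-based or bootstrap version for all outcomes as a sensitivity analysis, not as a data-driven substitute.

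The cost is analysis-plan wording and one additional prespecified sensitivity analysis. Baseline values, week-8 values and sex are already collected, so no extra patients, visits or samples are needed. The between-arm model also addresses the traditional-versus-modern objective in section 2.2.

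### Section 3.9 names only paired tests for numerical clinical and laboratory outcomes, so the traditional-versus-modern clinical objective has no between-arm analysis for them

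*Combined protocol and SAP*

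**What the plan says.** Section 2.2 lists as a specific objective: "Assess the impact of traditional bread versus modern bread on improving the clinical response of patients with quiescent UC". Sections 3.1 and 3.7 describe a randomised, double-blind trial with 48 patients per arm.

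The first paragraph of section 3.9 deals with demographics, questionnaires and numerical data. Pearson's chi-squared is to look for a "significant difference between demographics and questionnaire data with more than one category", without saying which groups are compared. For numerical data the rule is: "For data with normal distribution, a paired t-test will be used to determine whether there is a statistically significant difference". The Wilcoxon signed-rank exact test replaces it when normality fails.

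The second paragraph opens with alpha and beta diversity. Only there do two-sample tests appear: "statistical differences in each treatment group will be analysed using Welch two sample t-test or paired t-test", with the rank-sum or signed-rank test for non-normal data.

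Section 3.7 plans repeated measurement. At V0 "the different established questionnaires and indexes will be completed (Rome IV, Mayo, IBS-SSS, CVE-20, HADS"), and the same instruments plus a Likert rating are listed for the final visit. A blood test, with calprotectin, is listed at both. Entry under section 3.2 requires "symptomatology defined by Rome IV criteria and IBS Symptom Severity Score (IBS-SSS) > 175".

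**The concern.** A paired test asks whether patients changed between V0 and VF. The objective asks whether patients given one bread fared better than patients given the other, and only a comparison of the arms uses the randomisation to answer that.

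Followed as written, 3.9 leaves two options, and does not say which applies. Pooled over arms, the paired tests ignore the allocation and say nothing about bread type. Run per arm, they credit the bread with every change shared by both arms: natural course, expectation, attention from the study, and possibly regression to the mean after selection on a high symptom score. With no between-arm test fixed in advance, the choice between a within-arm and a between-arm claim could also be made after the results are seen.

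**Working it through.** **1. Which test reaches which variable.** The point turns on no figure in the plan, so there is none to reproduce. It rests on this reading:

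| Data | Test named in 3.9 | Compares the arms? |
|---|---|---|
| Demographics, categorical questionnaire items | Pearson chi-squared | Possible; groups not stated |
| Numerical clinical and laboratory data | Paired t, Wilcoxon signed-rank | No |
| Microbiota diversity | Welch or paired t; rank-sum or signed-rank | Possible with the two-sample tests |

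No ANCOVA, mixed model, arm-by-time term or two-sample test of change is named for the middle row.

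**2. What the paired tests estimate.** Write the mean change as C + T in the traditional arm and C + M in the modern arm, where C is common to both. The objective concerns T − M. The per-arm paired tests address C + T and C + M. The pooled test, with equal arms, addresses C + (T + M)/2. None isolates T − M. A two-sample comparison does, because C cancels.

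**3. How large C could be from selection alone.** From the documents: entry cut-off 175 (3.2), n = 48 per arm (3.7), significance level 0.05 (3.9). Assumed: two-sided testing; V0 is the qualifying score; unselected IBS-SSS is normal with mean μ = 150 to 300 and SD σ = 75 to 100; unselected V0-VF correlation r = 0.5 to 0.7; no bread effect.

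With a = (175 − μ)/σ, λ = φ(a)/(1 − Φ(a)) and v = 1 + aλ − λ²:
- mean fall = (1 − r)λσ
- SD of change = σ√[(1 − r)²v + 1 − r²]
- standardised fall d = mean fall / SD of change, tested by noncentral t with noncentrality d√48

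Example, μ = 200, σ = 75, r = 0.5: a = −0.333, λ = 0.5985, v = 0.4423. Fall = 0.5 × 0.5985 × 75 = 22.4. SD of change = 75 × √(0.25 × 0.4423 + 0.75) = 69.6. So d = 0.323, noncentrality 2.24, and the chance of a significant improvement in that arm is 59%.

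Over σ = 75-100 and r = 0.5-0.7, the chance that one arm of 48 appears significantly improved is:

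| Assumed unselected mean | One arm improved, no bread effect |
|---|---|
| 150 | 76-97% |
| 200 | 38-66% |
| 250 | 12-29% |
| 300 | 5-11% |

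The nominal rate in that direction is 2.5%.

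If V0 is instead a fresh score, equally correlated with the screening score as VF is, V0 and VF have the same expected value after selection. The mean change is then zero and the rate is about 2.5%. In simulation, between-arm ANCOVA and the two-sample test on change stayed at 2.3-2.7% in that direction under both versions of V0.

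**4. Illustration only: setting one per-arm p-value against the other.** The plan states no such rule. Suppose both arms truly change by the same d, and let p be the power of the paired test at n = 48. The pattern of a significant result for traditional bread and none for modern bread then has probability p(1 − p):

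| d | p | p(1 − p) |
|---|---|---|
| 0.2 | 0.274 | 0.199 |
| 0.3 | 0.530 | 0.249 |
| 0.4 | 0.775 | 0.175 |
| 0.5 | 0.924 | 0.070 |

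That is about 7-25%, against 2.5% for a valid between-arm test in that direction.

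**The case against.** The best defence is that a between-arm comparison is plainly intended and only unevenly written down. The Likert rating is listed only at the final visit, so a chi-squared test on it can hardly be before-after; arm against arm is the natural reading. Clinical response is not defined in 2.2 and could be a categorical outcome. Welch and rank-sum tests already stand in 3.9. All of this is fair, and the gap may be a drafting omission. It does not close the gap: nothing extends the two-sample tests to IBS-SSS, HADS, Mayo or the laboratory values, and the paragraph that covers those variables names only the paired family.

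A reader might infer more than the documents support:
- *That no clinical variable has a between-arm test.* Chi-squared may supply one for categorical items.
- *That the plan would report false improvement at a known, high rate.* No document gives an IBS-SSS mean, SD or correlation, and candidates must also meet Rome IV, so an unselected mean well above 175 is plausible. Section 3.7 also puts the eligibility check at a visit before V0. IBS-SSS is listed by name only from V0 on, so whether V0 is the qualifying score is unclear.
- *That the investigators will judge the breads by comparing two p-values.* The plan does not say so.

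**Conclusion.** The point stands, and the plan should be changed before analysis. As written, the stated clinical comparison of the two breads has no between-arm analysis for any numerical clinical or laboratory outcome. That conclusion comes from the text alone and needs no assumption.

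The size of the consequence is uncertain. False improvement from regression to the mean arises only if V0 is the qualifying score, or otherwise stands closer to it than VF does. Even then it runs from about 5% to 97% over the assumed inputs, so no single figure should be quoted as the plan's error rate. The 7-25% illustrates one possible misuse of per-arm results, not a rule in the plan.

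**What to change.** In section 3.9:
- State that numerical clinical and analytical outcomes are compared between arms. ANCOVA of the VF value on arm, V0 value and sex is preferred (section 3.5 randomises separately by sex), with the adjusted difference and its 95% CI.
- For markedly non-normal or bounded scores, such as Mayo (at most 2 at entry), use a rank-based between-arm test on change.
- State that within-arm V0-VF tests are descriptive only.
- State that chi-squared on categorical outcomes such as the Likert rating compares the arms.

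A two-sample test on change, extending the tests already named for diversity, would also cure the defect with some loss of precision. Under the selection model at mean 200, σ = 75 and 80% power, the detectable difference is 0.578 against 0.540 VF SD for ANCOVA at r = 0.5, and 0.503 against 0.484 at r = 0.7. In patients, that is (0.578/0.540)² = 1.15 and (0.503/0.484)² = 1.08, or about 15% and 8% more for the same power.

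The cost is wording. The scores and blood tests are already planned at both visits (triglycerides and cholesterol are listed in 3.6 but not named in the visit lists, which should be confirmed), and no extra patients are needed. The downside for the investigators is that within-arm p-values can no longer serve as evidence of benefit.
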